8.9.3 Medication Satisfaction Questionnaire

The MSQ is a single-item questionnaire that evaluates satisfaction with medication (Vernon 2010). It is a subject-completed instrument with the following response levels. Responses are ordinal but can also be categorized into satisfied (5-7), neutral (4), or dissatisfied (1-3). The MSQ has shown an acceptable reliability (ICC>0.80) and validity (known groups, convergent and divergent validity) based on a randomized controlled trial with 191 schizophrenia patients (Vernon 2010).

8.9.4 Work Productivity and Activity Impairment Questionnaire: Specific Health Problem (WPAI: SHP)

The impact of the disease and its treatment on work productivity and regular daily activities will be assessed by the WPAI Questionnaire (Reilly 1993). The WPAI questionnaire has 2 versions: WPAI-general health (WPAI-GH) and WPAI-Specific Health Problem (WPAI- SHP). In this study, WPAI-SHP will be used to target the measure to OUD. The WPAI-SHP has 6 items designed to measure employment, number of hours missed from work, and activity impairment during the past seven days due to the health problem. WPAI: SHP has been used among patients with OUD (Hoffman 2017).

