14.7.2.1 Health Economics & Outcomes Analyses

Treatment Effectiveness Assessment (TEA)

HEOR endpoints relating to the TEA will be described as change from baseline score to each follow-up assessment and end of treatment (EOT). Absolute scores by study visit will also be reported and compared between treatment groups. The absolute score and/or change from baseline score at EOT will be considered the primary variable of interest in these analyses.

Baseline will be defined as the last assessment on or before Week 3 Day 15±4 (Visit 4). (See Appendix 2- Treatment Clinic Schedule of Events)

MEDICATION SATISFACTION QUESTIONNAIRE (MSQ)

The percentage of subjects reporting each response on the MSQ will be reported by study visit and EOT. The percentage of subjects reporting that they are satisfied (score 5-7) at the EOT will be considered the primary variable of interest in these analyses.

WORK PRODUCTIVITY ASSESSMENT INSTRUMENT: SPECIFIC HEALTH PROBLEM (WPAI:SHP)

For the WPAI:SHP, the percentage of patients employed, percentage absenteeism, percentage work impairment, and percentage activity impairment will be reported at baseline, each follow-up assessment and EOT by treatment arm. The change in percent employed from baseline to each follow-up assessment will be assessed. Among those employed at baseline and the respective follow-up assessments, the changes from baseline in percentage absenteeism, percentage work impairment and percentage activity impairment at each follow-up assessment will be assessed. The change in percent employed from baseline to EOT; and among those employed at baseline and EOT, the changes in percentage absenteeism, percentage work impairment and percentage activity impairment from baseline to EOT will be considered as primary variables of interest in these analyses.

Baseline will be defined as the last assessment on or before Week 3 Day 15±4 (Visit 4). (See Appendix 2- Treatment Clinic Schedule of Events)

HEALTHCARE RESOURCE UTILIZATION QUESTIONNAIRE(HCRUQ)

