Frequency of use by HCRUQ type will be summed throughout the study period, from Week 1 to EOT (or last visit with available data for subjects who discontinue treatment prematurely), to arrive at a total use while in the study. The incidence of HCRUQ by type will be assessed, dividing by the total amount of follow-up time in each group. Types of hospitalisations, emergency room, and outpatient service visits will be categorized (e.g., medical, surgical, psychiatric). Hospital days will be calculated as the sum of all inpatient days during the study.

For continuous measures, 95% confidence intervals will be provided for comparisons of statistics between treatments. Unless otherwise specified, the absolute value of continuous outcome measures will be analysed using a mixed model for repeated measures (MMRM). A test of proportions (for example: exact test) will be used to evaluate treatment differences for categorical outcome variables.

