14.8 Handling of Missing Data

In general, missing data (caused by premature discontinuation or otherwise) will not be imputed. However, missing urine drug screen data will be imputed based on previously defined methods in other patient populations. The secondary endpoint is time attending clinic and patients failing to appear will be considered to have stopped attending at the date of last visit after they've missed 5 consecutive visits. Any missing covariates will be handled via appropriate multiple imputation techniques.

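### Change in WPAI:SHP activity impairment is limited to subjects employed at both time points, although the score covers regular daily activities and not only work

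*Combined protocol and SAP*

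**What the plan says.** Section 14.7.2.1 (WPAI:SHP) plans three kinds of result.

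- **Levels.** Percent employed and the three impairment scores are summarised over time. For activity impairment the text reads "percentage activity impairment will be reported at baseline, each follow-up assessment and EOT by treatment arm". It states no employment condition.
- **Change to each follow-up.** "Among those employed at baseline and the respective follow-up assessments, the changes from baseline in percentage absenteeism, percentage work impairment and percentage activity impairment" are to be assessed. A single condition governs all three scores.
- **Change to EOT.** The variables of interest for this questionnaire are the change in percent employed and, "among those employed at baseline and EOT, the changes in percentage absenteeism, percentage work impairment and percentage activity impairment from baseline to EOT".

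On the instrument, Section 8.9.4 says "The impact of the disease and its treatment on work productivity and regular daily activities will be assessed by the WPAI Questionnaire", and adds "The WPAI-SHP has 6 items designed to measure employment, number of hours missed from work, and activity impairment during the past seven days".

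Three other provisions bear on the point. The closing paragraph of Section 14.7.2.1 makes a mixed model for repeated measures (MMRM) on absolute values the default for continuous health-economics outcomes. Section 14.8 says "In general, missing data (caused by premature discontinuation or otherwise) will not be imputed". Section 14.4.1 defines the Treatment Population as everyone who received at least one dose and assigns it to all efficacy analyses.

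**The concern.** Absenteeism and work impairment describe what happens at work, so a change in either can be computed only for someone with a job at both times. Activity impairment, as Section 8.9.4 describes the instrument, concerns regular daily activities. Grouping the three scores in one clause gives activity impairment a restriction that it does not need.

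The consequence is more than a loss of numbers. Employment at follow-up is observed after treatment starts, and change in percent employed is itself a variable of interest in the same sentence. Conditioning on it makes the result describe subjects who held a job at both time points, and this need not match the treated population. A subject who was out of work at baseline and has regained both a job and daily function by EOT would be missing from the change analysis. So would a subject who lost a job as function declined.

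**Working it through.** The documents state no sample size, precision or employment figure for the WPAI, so there is no planned figure to reproduce. The check is a reading of the text, followed by an illustration on stated assumptions.

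**Step 1: does each score need a job?**

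| Score | Needs a job at both times? | Condition in 14.7.2.1 |
|---|---|---|
| Absenteeism | Yes | Employed at both times |
| Work impairment | Yes | Employed at both times |
| Activity impairment | Not on the description in 8.9.4 | Employed at both times |

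**Step 2: who is left out of the activity-impairment change?** For a given comparison, subjects fall into four groups by job status at baseline and at follow-up.

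- Employed, employed: kept.
- Employed, not employed: left out.
- Not employed, employed: left out.
- Not employed, not employed: left out.

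Employment is not an eligibility criterion in Sections 5.2 and 5.3, so all four groups can occur. The general rule against imputation in Section 14.8 does not bring the last three back.

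**Step 3: is there an unrestricted change analysis elsewhere?** None is stated. The levels are unrestricted, but every stated change in activity impairment carries the condition.

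**Step 4: illustrative size.** Let *e* be the share of subjects with paired scores who are employed at both times. Then

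- share left out = 1 − *e*
- standard-error ratio, restricted to full set = √(1/*e*), assuming the same SD in both sets.

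| *e* (assumed) | Left out | SE ratio |
|---|---|---|
| 0.20 | 80% | 2.24 |
| 0.30 | 70% | 1.83 |
| 0.40 | 60% | 1.58 |
| 0.50 | 50% | 1.41 |
| 0.60 | 40% | 1.29 |

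Job loss lowers *e* further. If 20% were employed at baseline and 70% of them kept the job, *e* = 0.20 × 0.70 = 0.14. Then 86% would be left out, with a ratio of √(1/0.14) = 2.67. These figures measure lost precision only. The selection effect comes on top, and the documents give nothing from which to judge its size or direction.

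**The case against.** **The excluded subjects are still analysed.** A reader might infer that an unemployed subject contributes nothing to the activity-impairment results. The documents do not support that. Section 14.7.2.1 reports levels at baseline, each follow-up and EOT with no employment condition, and the default MMRM on absolute values would take in the same subjects. Those who gain or lose a job also count in the change in percent employed. This objection stands and confines the point to the change variable. It does not remove the point, because the variable singled out as of primary interest is the restricted change.

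**The schedule makes the rule moot.** Appendix 2 lists the WPAI:SHP only at Visit 2. Visits 12, 17 and EOT carry an Employment Question instead. Taken literally, no subject has a follow-up activity-impairment score, and neither the restriction nor its removal alters a result. This stands as a limit on practical effect. Section 14.7.2.1 nevertheless plans follow-up analyses, and restoring the questionnaire at those visits would leave the wrong analysis set in place.

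**Size and availability are not documented.** A reader might infer that most of the data are lost, or that the activity score is available for everyone. Neither is established. With *e* = 0.60 only 40% are left out. Section 8.9.4 gives no item wording, skip pattern or scoring rule that would show who answers the activity item.

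**The stakes are low.** The WPAI belongs to the last-listed exploratory endpoint (Section 3.3), whose wording names employment, presentism and absenteeism but not activity impairment, and it does not appear in Table 2. The controls come from anonymised records, with no stated WPAI collection. All of this stands and sets the priority.

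**Conclusion.** The point holds for the change in activity impairment, both at each follow-up and at EOT. The employment condition has no basis in the documents for a score that covers regular daily activities. It selects on a post-treatment outcome and reduces precision. If 20% to 60% of subjects are employed at both times, with equal SD, 40% to 80% of those with paired scores are left out and the standard error is about 1.3 to 2.2 times larger. The employment range is an assumption. The finding about the analysis set does not depend on it.

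The point does not extend to the absolute summaries, the default MMRM or the two work scores. It has no bearing on the trial's primary endpoint: the label of primary interest applies only within the WPAI analyses. A reader might also infer that the restricted result must look too favourable because it keeps the most stable subjects. The documents give no data on the direction of any bias. This is a low-priority correction to an exploratory analysis.

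**What to change.** In both change sentences of Section 14.7.2.1 (each follow-up, and EOT):

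1. Apply the employed-at-both-times condition to absenteeism and work impairment only.
2. Derive the change in activity impairment in all Treatment Population subjects with a baseline and a follow-up WPAI:SHP activity score, whatever their employment.
3. If the employed-only result for activity impairment is wanted, keep it as a labelled supplementary summary.

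Reconcile Appendix 2 with Section 14.7.2.1 at the same time. Either the full WPAI:SHP is scheduled at the follow-up visits and EOT, or the follow-up WPAI analyses are withdrawn and the Employment Question is analysed for what it collects. In the second case this correction is no longer needed.

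The edit to the analysis text is a few words in two sentences and needs no data beyond the questionnaire. Any real cost lies in the schedule: if the WPAI:SHP is restored at follow-up, subjects complete six items at those visits.

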[figure not shown]
The primary analysis will be performed on the primary and key secondary endpoints after all subjects have been enrolled and completed the end of treatment visit. An enrolled subject is defined as a subject who has received at least one dose of SUBLOCADE.

STUDY SCHEMATIC

[figure not shown]
Figure 1 Study Schematic for SUBLOCADE Initiated in Emergency Department

- Participants who decline to be enrolled in the study will receive care as determined by the ED physicians and continue to be passively followed for 24 weeks. Passive follow-up will include tracking for treatment initiation and engagement and repeat OD via anonymized medical records and tracking for death using state death registries.
- Injection 2 will be 300 mg and will occur on Day 8 (-0 /+4 days); Injections 3-7 will remain 300 mg (or 100 mg if unable to tolerate 300 mg as determined by study investigator) administered at 28-day (-2/+4 days) intervals.
- Intervention subjects will receive a safety follow-up telephone call 30 days after their EOT/ET visit to assess AEs, SAEs, pregnancy status (if applicable) and concomitant medications. Subjects who decline to continue in MAT will receive monthly safety follow-up phone calls for an additional 5 months (6 months total) to assess SAEs, pregnancy status (if applicable) and concomitant medications.

Figure 2 Study Schematic for SUBLOCADE Initiated in Inpatient Unit

- Participants who decline to be enrolled in the study will receive follow-up care as determined by the inpatient unit physicians and continue to be passively followed for 24 weeks. Passive follow-up will include tracking for treatment initiation and engagement and repeat OD via anonymized medical records and tracking for death using state death registries.
- Injection 2 will be 300 mg and will occur on Day 8 (-0/+ 4); Injections 3-7 will remain 300 mg (or 100 mg if unable to tolerate 300 mg as determined by study investigator) administered at 28-day (-2/+ 4 days) intervals.
- Intervention subjects will receive a safety follow-up telephone call 30 days after their EOT/ET visit to assess AEs, SAEs, pregnancy status (if applicable) and concomitant medications. Subjects who decline to continue in MAT will receive monthly safety follow-up phone calls for an additional 5 months (6 months total) to assess SAEs, pregnancy status (if applicable) and concomitant medications.

Figure 3 Study Schematic for Initial Dose of SUBLOCADE in Clinic

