3.3 Exploratory

The exploratory endpoints of this study are:

- Opioid craving in subjects as measured by Craving Visual Analog Scale (VAS) scores.
- Illicit opioid use as measured by urine drug screen (UDS) results.
- Genetic predictors of treatment response and OD.
- Predictability of treatment response based on impulse control as measured by decision making in the delay discounting task, and opioid cravings/valuation as measured by the brief opioid demand task.
- Numbers of ED and hospital visits compared to the historical control (2015-2018) obtained from VCU anonymized health records.
- Scores on Treatment Effectiveness Assessment (TEA), medication satisfaction as measured by the Medication Satisfaction Questionnaire (MSQ), and employment, presentism and absenteeism as assessed by the Work Productivity and Activity Impairment Questionnaire: Specific Health Problem (WPAI:SHP).

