6.4 Withdrawal and Stopping Criteria

6.4.1 Subject Withdrawal from Treatment

A subject will be considered withdrawn from treatment if the subject has permanently discontinued study treatment. The primary reason for withdrawal from treatment must be entered into the electronic case report form (eCRF) (e.g., death, AE, protocol non-compliance, investigator's decision, or as requested by the subject for another or unknown reason). Subjects who discontinue study treatment for any reason other than lost to follow-up will continue to be followed on an approximately monthly basis by telephone for repeat OD and treatment status and any scheduled HEOR assessments through to the end of their scheduled 30-day safety follow up telephone call.

Subjects who are withdrawn from the study for any reason after treatment with SUBLOCADE will not be replaced.

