6.4.4 Subjects Lost to Follow-up

In cases of a missed visit, the Investigator or designee must attempt to contact the subject and re-schedule as soon as possible. The Investigator or designee must counsel the subject on the importance of maintaining the assigned visit schedule and ascertain whether or not the subject wishes to and/or should continue in the study.

In the event a subject misses 5 consecutive weeks' worth of visits, they will be considered to have ceased treatment and withdrawn from the study. Investigators or designees must make a reasonable effort to contact the subject. Two documented attempts (e.g., phone, email, etc.) to contact the subject followed by a certified mailed letter is considered reasonable. Subjects who can no longer be contacted will be considered lost to follow-up.

For the purpose of documenting date of discontinuation for a subject confirmed to be lost to follow-up, the date of discontinuation will be the date of last in-person visit.

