8.9.2 Healthcare Resource Utilization Questionnaire (HCRUQ)

The HCRUQ will be completed by the Investigator or qualified designee and will collect hospitalizations; residential substance abuse treatment; general practitioner, specialist, and counselling visits; and Emergency Department (ED) visits. Also, The HCRUQ information will be obtained from informatics and electronic medical records from the respective site. It will

include information on medical services provided in the inpatient, outpatient, emergency department and other ancillary services available within the site's network.

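### Healthcare use after early discontinuation is cut off in the SUBLOCADE group, but the health-record controls have no matching window, so the two sides of the ED and hospital-visit comparison do not cover the same period

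*Combined protocol and SAP*

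**What the plan says.** The HCRUQ paragraph of Section 14.7.2.1 sums each type of use from Week 1 to EOT, "or last visit with available data for subjects who discontinue treatment prematurely". It reports that sum as total use in the study, adds up inpatient days, and obtains an incidence by "dividing by the total amount of follow-up time in each group".

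The endpoint in Section 3.3 is a comparison between groups: "Numbers of ED and hospital visits compared to the historical control (2015-2018) obtained from VCU anonymized health records". The matching objective in Section 2.3 extends the controls from 2015 to the end of data collection. Section 13.1.1 describes the control source as an anonymized record extract and sets no window for healthcare use. The notes to the study schematics say that decliners "continue to be passively followed for 24 weeks". They list treatment initiation and engagement, repeat OD and death as the items tracked, and do not mention healthcare use in general.

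Four other places bear on treated subjects:

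- Section 8.9.2: besides the questionnaire, "The HCRUQ information will be obtained from informatics and electronic medical records from the respective site".
- Section 6.4.1: subjects who stop treatment, unless lost to follow-up, are telephoned about monthly, with "any scheduled HEOR assessments through to the end of their scheduled 30-day safety follow up telephone call". Section 3.5 lists the HCRUQ among the health economics assessments.
- Section 6.4.4: after five consecutive weeks of missed visits, "they will be considered to have ceased treatment and withdrawn from the study". For those confirmed lost, "the date of discontinuation will be the date of last in-person visit".
- Section 14.7.1: primary events are counted over six months in every treated subject, with no cut at treatment stop.

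**The concern.** The two sides of the comparison are not counted over the same period. A treated subject's contribution ends when attendance or contact ends. A control's contribution comes from records that do not depend on attending a study clinic, and no end point tied to treatment is stated for it.

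This affects two kinds of output differently. Section 3.3 asks for numbers of visits, and Section 14.7.2.1 asks for total use and summed hospital days. These have no denominator, so any use after the cut-off is simply lost from the SUBLOCADE side. The incidence does have a denominator, so the matching person-time is dropped too. What remains there is a rate over a different, attendance-dependent window: early time in those who leave and full time in those who stay, against a control rate over an undefined window. A published statement about ED and hospital use could rest on that mismatch.

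**Working it through.** The plan states no figure for this comparison, so there is none to reproduce. The sample size in Section 14.2 rests on repeat OD or death and does not depend on this rule. The documents give no dropout rate and no visit rates. Every input below is an assumption except the 24-week (168-day) length and the early clustering of repeat events described in the Synopsis rationale.

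**Step 1: literal cut-off, constant rates.** Let T = 168 days. A share d stops at day t, and the visit rate after stopping is k times the rate before.

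- Share of treated visits omitted = d·k·(T−t) / [(1−d)T + d·t + d·k·(T−t)]
- Observed rate / full-window rate = T / [(1−d)T + d·t + d·k·(T−t)]

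With d = 0.40 and t = 56, (1−d)T = 100.8, d·t = 22.4 and d(T−t) = 44.8.

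| k | Visits omitted | Observed / full-window rate |
|---|---|---|
| 0.5 | 22.4/145.6 = 15.4% | 168/145.6 = 1.15 |
| 1 | 44.8/168 = 26.7% | 168/168 = 1.00 |
| 2 | 89.6/212.8 = 42.1% | 168/212.8 = 0.79 |

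Over d = 20–60%, t = 28–84 days and k = 0.5–3, the omitted share runs from about 5% to 75% and the rate ratio from 1.33 down to 0.50. Totals always fall. The rate moves either way.

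**Step 2: allow for early clustering.** The Synopsis rationale says 70% of second events fell within 6 months of the index OD and most fell in the first 2 months. If most refers to the 6-month events, the first-2-month share f exceeds 50%. If it refers to all second events, f exceeds 0.50/0.70 = 71% of the 6-month events. Assume that visits follow the same pattern, that the on-treatment rate is half the control rate, that the off-treatment rate equals the control rate, and that a share d stops at month 2. Set control use over 6 months to 1.

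- Counted under the rule: A = 0.5(1−d) + 0.5·f·d, over M = 6(1−d) + 2d months
- Full window: B = 0.5(1−d) + d[0.5·f + (1−f)]
- Rate ratio to control under the rule = 6A/M; over the full window = B; share omitted = 1 − A/B

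| f | d | A | B | Omitted | Ratio, rule | Ratio, full window |
|---|---|---|---|---|---|---|
| 1/3 (flat) | 30% | 0.40 | 0.60 | 33% | 0.50 | 0.60 |
| 1/3 (flat) | 50% | 0.333 | 0.667 | 50% | 0.50 | 0.67 |
| 1/3 (flat) | 60% | 0.30 | 0.70 | 57% | 0.50 | 0.70 |
| 0.51 | 50% | 0.3775 | 0.6225 | 39% | 0.57 | 0.62 |
| 0.60 | 30% | 0.44 | 0.56 | 21% | 0.55 | 0.56 |
| 0.60 | 50% | 0.40 | 0.60 | 33% | 0.60 | 0.60 |
| 0.60 | 60% | 0.38 | 0.62 | 39% | 0.63 | 0.62 |
| 0.70 | 50% | 0.425 | 0.575 | 26% | 0.64 | 0.58 |

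With a flat rate the rule flatters SUBLOCADE. At f = 0.60 the rate bias almost vanishes, and at f = 0.70 it reverses. The loss from raw totals persists in every row, including the row where the two rates agree (d = 50%, f = 0.60: one third of visits omitted).

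**The case against.** A reader might infer that all use after dropout is discarded on the treated side only, and that this must favour SUBLOCADE, by more as dropout rises. The documents do not support that.

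- The cut-off is the last visit with data, not the last injection. Sections 6.4.1 and 8.9.2 provide for telephone assessments and medical-record data after treatment stops. Whether a telephone call or a later record entry counts as a visit is not said, so complete omission is not established. It is clearest for subjects lost to follow-up, whom Section 6.4.1 excludes from the calls and Section 6.4.4 dates back to the last in-person visit.
- The absence of a cut-off for controls rests on silence. Nor can controls be described as never treated: decliners are tracked for starting treatment, and Section 14.2 calls the historical group treatment as usual.
- The direction of bias in the rate is not settled. If the drug works as Section 3.6 hypothesises, use should rise after stopping, which would make the treated rate too low. Early clustering pulls the other way, because censoring keeps the high-risk months and drops the quieter ones.

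All three points stand, and they limit the claim. They do not remove the loss from raw totals and hospital days, and they do not give the two groups a common window. The endpoint is also exploratory, and the primary endpoint already uses a six-month rule for all treated subjects.

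**Conclusion.** The concern holds in a limited form. As written, Section 14.7.2.1 truncates visit totals and hospital days in the SUBLOCADE group whenever use occurs after the cut-off. It also compares an attendance-dependent treated rate with a control rate whose window is undefined. With 40% dropout at day 56 and an unchanged visit rate, about 27% of treated visits would be missing from the totals. Across the constant-rate assumptions tried, the range is about 5% to 75%. These figures take the cut-off literally and would shrink to the extent that telephone or record data after treatment stop are counted.

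No size or direction can be given for the rate. Its bias depends on dropout, on use after dropout and on how early visits cluster, and the documents supply none of these for healthcare use. The early clustering they describe concerns repeat OD and death, so applying it to all visits is itself an assumption. No primary or key secondary conclusion is affected. Priority is low.

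**What to change.** For the comparison with controls, rewrite the HCRUQ paragraph of Section 14.7.2.1 as follows:

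1. Count ED visits, hospitalisations and hospital days from VCU electronic records only. The questionnaire has no counterpart in the controls.
2. Use one fixed window of about 6 months (24 weeks) with the same start point, for example the index OD, for treated subjects, historical controls and concurrent controls. Treat the index visit or admission identically in all groups. State the length in days: Appendix 2 puts EOT at day 169, while Section 4.2 puts it at 7 months.
3. Keep counting regardless of treatment discontinuation or loss to follow-up. End early only at death or where withdrawal of consent (Section 6.4.3) bars use of the records.
4. Remove the early cut-off for these record-based items. Report questionnaire-only items, such as general practitioner and counselling visits, as a description within the SUBLOCADE group.
5. Reconcile the paragraph with Sections 6.4.1, 8.9.2 and 14.7.1, and align the control period between Sections 2.3 and 3.3.

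The cost is SAP wording and minor extra analysis from a record source the plan already names. The utilisation estimate may move in either direction.
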